6.3.1 Study Schedule

There will be five expected study visits or encounters:

Study Encounter #1	
 • Screening and consent • Enrollment and randomization • Assess subject's baseline pain level using visual analog scale • Administer Edinburgh Postnatal Depression Scale to establish baseline • Administer Infant Feeding Intention Survey to establish baseline • Administer EQ-5D questionnaire to establish baseline • Initiation of assigned intervention • Assess subject's pain level two hours after intervention start using visual analog scale • Plasma and urine samples will be collected at Yale site • Milk samples will be collected 	During hospitalization for induction of labor
Study Encounter #2	
 • Assess subject's pain experienced during childbirth with visual analog scale • Administer Labour Agency questionnaire • Administer Birth Satisfaction Scale-Revised questionnaire • Administer EQ-5D[™] questionnaire • Administer EQ-TIPS[™] questionnaire • Milk samples will be collected up to twice a day (if applicable) postpartum 	During hospital postpartum stay prior to discharge
Study Encounter #3	
 • Administer PIMS questionnaire • Administer EQ-5D[™] questionnaire • Administer EQ-TIPS[™] questionnaire 	Contacted by email or text message 2 weeks postpartum

Study Encounter #4	
 • Administer Maternal Breastfeeding Evaluation Scale (MBES) questionnaire to all subjects who report at least one attempt at breastfeeding during the postpartum period. • Administer Edinburgh Postnatal Depression Scale questionnaire • Administer EQ-5D[™] questionnaire • Administer EQ-TIPS[™] questionnaire 	Contacted by email or text message 4-12 weeks postpartum
Study Encounter #5	
 • Administer short questionnaire to assess infant feeding method • Administer EQ-5D[™] questionnaire • Administer EQ-TIPS[™] questionnaire 	Contacted by email or text message 6 months postpartum

6.3.2 Informed Consent

Informed consent will be obtained by trained study personnel who are qualified to obtain informed consent. Informed consent will be obtained in a private room, free of distraction, on the Labor and Birth Units at study sites. A full explanation of study procedures will be provided to the subject and all subjects will be given the opportunity to ask questions. All questions will be answered to the best of the ability of study personnel, and if queries are made that cannot be addressed at that time, the site investigators will be asked to respond. The subject will be notified of the IRB contact should she have any questions. The subject's level of comprehension will be assessed by study personnel, and if not sufficient to assure that consent is truly informed, additional information will be provided. Patients will be informed that study participation is voluntary to minimize undue influence or coercion and they will be offered sufficient time to review the study prior to obtaining their informed consent. Women will be given ample time to review the consent, ask questions, and discuss with their partners (if applicable) before deciding to enroll in the study. Women ages 18+ will be enrolled, so parental permission is not required. Women will only be included if they are English or Spanish speaking. We do have study consent personnel who are fluent in Spanish. If there is no available research member who is fluent in Spanish, we will use a hospital phone interpreter to review the consent form and study information with the patient. If another person is with the woman during this process, she will be asked if she would like to discuss the study on her own or together with the accompanying person or people.

Informed consent will be documented with the subject's signature and date. Subjects will be provided with a copy of the informed consent form. The form will be placed in the subject's coded chart, which will be maintained in a location separate from any clinical care

documents and will be coded with an alphanumeric code. This code will be the subject's unique identifier that will carry through the entire study.

6.3.3 Screening

All patients who are scheduled for an induction of labor or are admitted to the hospital's labor and birth unit to undergo induction of labor will be screened for study eligibility by a trained member of the investigative team. With the assent of their primary obstetric physician or midwife, patients meeting eligibility criteria will be approached for potential recruitment. The study will be explained in detail and all questions will be answered prior to signing written informed consent to participate in the study. Screening will occur before planned exogenous oxytocin intravenous infusion has been initiated.

6.3.4 Recruitment and Enrollment Procedures

A certified member of the investigative team will review the list of patients admitted to the labor and delivery unit for labor induction and assess their eligibility using the inclusion and exclusion criteria. A partial waiver of consent will be obtained to allow review of their medical chart to ensure their eligibility prior to approaching patients. A certified member of the team will enroll a consented subject into the study. The subject will be randomized to a study arm with RedCap database, and the assigned intervention will be initiated. All study data will be entered into the RedCap database.

6.3.5 On Study Visits

Study Encounter #1	
 • Screening and consent • Enrollment and randomization • Assess subject's baseline pain level using visual analog scale • Administer Edinburgh Postnatal Depression Scale to establish baseline • Administer IFI Survey to establish baseline • Administer EQ-5D questionnaire to establish baseline • Initiation of assigned intervention • Assess subject's pain level two hours after intervention start using visual analog scale • Milk samples will be collected 	During hospitalization for induction of labor	40 minutes
--------------------	--	---	------------

Study Encounter #2	
 Assess subject's pain experienced during childbirth with visual analog scale Administer Labour Agency questionnaire Administer Birth Satisfaction Scale-Revised questionnaire Administer EQ-5D[™] questionnaire Administer EQ-TIPS[™] questionnaire Milk samples will be collected up to twice a day (if applicable) postpartum 	During hospital postpartum stay prior to discharge	40 minutes
Study Encounter #3	
 Administer PIMS questionnaire Administer EQ-5D[™] questionnaire Administer EQ-TIPS[™] questionnaire 	Contacted by email or text message 2 weeks postpartum	15 minutes
Study Encounter #4	
 Administer Maternal Breastfeeding Evaluation Scale (MBES) questionnaire to all subjects who report at least one attempt at breastfeeding during the postpartum period Administer Edinburgh Postnatal Depression Scale questionnaire Administer EQ-5D[™] questionnaire Administer EQ-TIPS[™] questionnaire 	Contacted by email or text message 4-12 weeks postpartum	30 minutes
Study Encounter #5	
 Administer short questionnaire to assess infant feeding method Administer EQ-5D[™] questionnaire Administer EQ-TIPS[™] questionnaire 	Contacted by email or text message 6 months postpartum	10 minutes

6.3.6 End of Study and Follow-up

The study will be concluded when the planned sample size of women has been enrolled, randomized, have delivered, and the last subject to deliver is past the 6-month postpartum timepoint, and all planned data have been collected.

If a subject withdraws from the interventional portion of the study but agrees to continued follow-up of associated clinical outcome information (as described in the original informed consent form), these data will be collected from the medical record. If a subject withdraws

from the interventional portion of the study and does not consent to continued follow-up of associated clinical outcome information, we will not access for purposes related to the study, the subject's medical record or other confidential records requiring the subject's consent.

6.3.7 Removal of subjects

Subjects will be informed that they may withdraw from the study at any time for any reason, without prejudice to their medical care. The investigators also have the right to withdraw subjects from the study for the following reasons: non-adherence to the protocol requirements (both in the intrapartum nipple stimulation and exogenous oxytocin infusion arms) by the subject or the subject's primary maternity care provider, or the subject no longer meets the protocol eligibility criteria. If a subject withdraws from the study, the primary reason for a subject's withdrawal will be recorded in the data collection. Subject who withdraw or are withdrawn from the study will not be replaced. If immediate deviation from the protocol is required to eliminate an immediate hazard(s) to subjects, the investigators will contact the IRB, if circumstances permit, to discuss the planned course of action. Any departures from the protocol must be fully documented. Unplanned protocol deviations will be reported to the IRB per institutional requirements. If the opinion of the study Principal Investigator ([name]) is that there is sufficient reasonable cause for premature study termination, written notification documenting the reason(s) for study termination will be provided to the IRB. If a subject withdraws from the study, the data collected on the subject to the point of withdrawal will remain part of the study database and will not be removed. Removal of already collected data would undermine the scientific, and therefore the ethical, integrity of the research. Incomplete data could potentially put enrolled study subjects and future study subjects at unreasonable risk as a result of inaccurate data/conclusions.

If a spontaneous labor control patient develops labor complications including prolonged or arrested labor requiring IV oxytocin or cesarean delivery, vaginal bleeding, or fetal heart rate decelerations requiring resuscitative efforts by the primary obstetric provider, biospecimens will not be collected at the time of entering active labor. The initial sample will still be used and medical records will still be reviewed unless the patient opts to withdraw from participation.

If a subject randomized to nipple stimulation withdraws from her intervention, her maternity care provider will be informed so the subject can be transitioned to routine obstetric care (e.g. initiation of exogenous oxytocin infusion).

If a subject withdraws, biological specimens that have not yet been analyzed will be destroyed and not analyzed further.

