The use of amniotomy (if the subject has intact membranes) and other labor procedures will be at the discretion of each subject's responsible maternity care provider (pragmatic study) and considered standard of care. If standard of care is altered based on clinical decision making by the subject's responsible treating physician or midwife, the subject will still remain in the study as long as the subject does not withdraw her consent to continue in the study.

5. Subject Management and Follow-Up

All subjects will be monitored for progression of labor and their fetus' response to labor by their responsible treating obstetrician or midwife. Each subject will undergo individualized assessment by their treating obstetrician or midwife, and the clinical decision will be made by the treating obstetrician or midwife if or when subjects in the nipple stimulation arm will be switched to the standard of care with exogenous oxytocin administration. There can be no absolute cut-offs for time or contraction responses since standard of care dictates individualized assessments for labor progression and fetal response; each birth experience is unique. Subjects in both arms of the trial should be allowed adequate time to labor before considering the induction "failed" and proceeding to cesarean section. An induction will be considered "failed" after at least 24 hours of exogenous oxytocin administration has failed to generate regular (e.g., every 3 minutes) contractions and cervical change, as is considered standard of care (36). Additionally, exogenous oxytocin generally should be administered for at least 12 hours after membrane rupture before considering the induction to have failed as is considered standard of care. (37). The time devoted to cervical ripening and/or nipple stimulation will not be included when calculating the length of induction for diagnosing failed induction.

It is expected that the fetal heart rate and uterine activity will be monitored continuously during labor and that subjects will stay in the hospital until delivery once the induction is started as is considered standard of care. Aside from the interventions described above, labor and delivery management decisions will be left to the discretion of the subject's responsible maternity care provider as is considered standard of care.

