6.4 Statistical Method

6.4.1 Statistical Design

Data analyses will adhere closely to the CONSORT guidelines. (27) Analyses will follow the intention-to-treat principle in which subjects will be analyzed in the group to which they were randomized, regardless of whether or not they received the assigned intervention.

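### Investigators may withdraw randomised women from the study for non-adherence or lost eligibility, in conflict with section 6.3 and intention-to-treat, with no provision to collect delivery mode afterwards

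*Protocol*

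**What the plan says.** Section 6.3.7 of the protocol provides: "The investigators also have the right to withdraw subjects from the study for the following reasons: non-adherence to the protocol requirements". After a parenthesis stating that this applies in both arms, the grounds continue: "by the subject or the subject's primary maternity care provider, or the subject no longer meets the protocol eligibility criteria". On what follows a withdrawal, the same section says "Subject who withdraw or are withdrawn from the study will not be replaced" and, where a subject withdraws, "the data collected on the subject to the point of withdrawal will remain part of the study database and will not be removed".

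Other sections point the other way:

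- Section 6.4.1, repeated in 6.4.3.1, sets the analysis principle: "subjects will be analyzed in the group to which they were randomized, regardless of whether or not they received the assigned intervention". Section 5.1 also commits to intention-to-treat.
- Section 6.3, item 4, deals with a treating clinician who departs from standard care: "the subject will still remain in the study as long as the subject does not withdraw her consent".
- Section 6.3.6 continues chart follow-up for a subject who withdraws "from the interventional portion of the study but agrees to continued follow-up of associated clinical outcome information".

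**The concern.** Section 6.3.7 allows withdrawal from the study, not merely from the assigned method. The same section treats a woman who gives up her intervention separately, so the protocol itself distinguishes the two. The trial is open label, so whoever exercises the right knows the arm and can see how labour is going.

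The primary outcome, spontaneous vaginal delivery, is known only at delivery. Non-adherence arises before that. If a woman is withdrawn in between and her chart is not followed, her primary outcome is missing for a reason that may be related to that outcome. Intention-to-treat then has nothing to analyse for her except an imputed value. Section 6.4.5 offers multiple imputation only as needed, and imputation from recorded covariates may not capture why an investigator chose to withdraw her. What is at stake is bias in the primary comparison, much more than power.

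**Working it through.** **1. Can the passages govern the same woman?** Take a woman in either arm whose clinician departs from the assigned management.

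- Section 6.3, item 4: she stays unless she withdraws consent.
- Section 6.3.7: the investigator may withdraw her, because non-adherence by the provider is a listed ground.
- Sections 6.4.1 and 6.4.3.1: she is analysed as randomised, whatever she received.

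The first two rules give opposite answers wherever the clinician's decision is also non-adherence. The third can be met from observed data only if her delivery is still recorded.

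**2. Is her delivery still recorded?**

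- Section 6.3.7 keeps what was collected before withdrawal and does not mention later data.
- Section 6.3.6 continues chart follow-up only where the subject herself leaves the interventional part and agrees.
- For the non-randomised spontaneous-labour controls who develop complications, 6.3.7 does say that record review continues. Randomised women withdrawn by an investigator have no equivalent sentence.

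So collection after an investigator's withdrawal is neither forbidden nor provided for.

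**3. The plan's own sample size.** Inputs from section 6.4.2: 64% versus 74%, two-sided alpha 0.05, 90% power, 5% attrition.

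- Uncorrected, per arm: n0 = [1.960 × √(2 × 0.69 × 0.31) + 1.282 × √(0.64 × 0.36 + 0.74 × 0.26)]² / 0.10² = 448 after rounding up.
- With continuity correction: n = (448/4) × [1 + √(1 + 4/(448 × 0.10))]² = 468 per arm, 936 in total.
- With attrition: 936/0.95 = 986, against 988 stated. The figure reproduces to within 2.

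Power without continuity correction is 92.6% with all 988 outcomes, 91.3% with 5% lost and 89.8% with 10% lost. Moderate loss costs little power, and the attrition allowance does nothing about bias.

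**4. Size of a possible bias (illustration).** Let a fraction f of one arm be removed, with spontaneous vaginal delivery rate r among those removed, and a true rate of 64% in both arms. The shift in the observed difference is

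shift = (0.64 − f × r)/(1 − f) − 0.64 = f × (0.64 − r)/(1 − f).

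Only two inputs come from the documents: the 64% control rate (6.4.2) and 1 of 18 = 5.6%, the stimulation-arm departure rate in the pilot (2.1). One-arm removal, the 10% and every value of r are assumptions.

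| f removed (of 494) | r = 40% | r = 30% |
|---|---|---|
| 5.6% (about 27 women) | 0.0556 × 0.24/0.9444 = +1.4 points | 0.0556 × 0.34/0.9444 = +2.0 points |
| 10% (about 49 women) | 0.10 × 0.24/0.90 = +2.7 points | 0.10 × 0.34/0.90 = +3.8 points |

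For the two-sided error rate, divide the shift by SE = √[p(1 − p)(1/n1 + 1/494)], where n1 is the number left in the reduced arm and p the pooled observed rate. With r = 40%:

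- 5.6% removed: n1 = 466.6, SE = 0.0309, ratio 0.458, error about 7.4%.
- 10% removed: n1 = 444.6, SE = 0.0311, ratio 0.857, error about 14%.

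With 10% removed and r from 54% down to 34%, the shift runs from +1.1 to +3.3 points and the error from about 6.5% to 19%.

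**5. Dependence on the one-arm assumption.** If the same f and r apply in both arms, the shifts cancel under the null. If removal falls on the oxytocin arm only, the shift has the same size and the opposite sign.

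**The case against.** The strongest reply is that this is a loosely worded administrative clause inside a plan whose analysis principle is stated correctly three times. Much of that reply stands, and it rules out several stronger readings that a reader might infer.

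- **That data stop, or are deleted, at withdrawal.** The documents do not say so. Section 6.3.7 is a retention rule and forbids removing collected data. On later data it is silent for women withdrawn by an investigator.
- **That ordinary labour progress makes a woman ineligible.** The dilation and fetal-tracing criteria in 5.3.2 are tied to the time of enrolment, so later events do not clearly breach them. Section 6.1.2 suggests a natural meaning, a re-check before assignment. The ground is still badly fixed, because 6.3.7 does not limit it to the period before randomisation.
- **That non-adherence falls mainly in the stimulation arm.** The pilot in 2.1 had 1 departure of 18 with stimulation and 1 of 6 with oxytocin. These numbers are tiny and give no support to that claim. Section 6.3.7 names both arms.
- **That clinician-directed switches would be removed as non-adherent.** Sections 6.1.3 and 6.3, item 5, leave much of that decision to the treating clinician, and 6.4.3.1 plans a sensitivity analysis of cross-overs, which presupposes that their outcomes are held. This narrows the group exposed to withdrawal. It also shows that non-adherence is undefined.

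The right is also discretionary, so it may never be used. None of this removes the conflict between 6.3.7 and 6.3, item 4, or supplies the missing provision for outcome collection. A statistical analysis plan, which is not at hand, could define analysis sets, but it cannot recover outcomes that were never abstracted.

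**Conclusion.** The point holds as an unreconciled conflict and a gap. The protocol gives unblinded investigators a right to withdraw randomised women from the study on grounds that arise before the primary outcome, and does not secure the outcome for those women. Informative loss is a risk of using that right and not a stated consequence.

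No number in the protocol is wrong on this point. Under the assumed scenario of one-arm removal, 64% in both arms and 40% among those removed, the shift is +1.4 to +2.7 points for 5.6% to 10% removed, against a 10-point design target. A lower assumed rate enlarges it, balanced removal cancels it, and removal from the other arm reverses it. The documents do not show how often the right has been used, so the actual effect cannot be estimated and could be nil.

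**What to change.** Amend 6.3.7 so that it agrees with 6.3 (item 4), 6.3.6 and 6.4.1:

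- Non-adherence, or a later change in eligibility status, ends at most the assigned study procedures and is not a ground for ending outcome collection.
- Delivery mode and the other chart outcomes are abstracted for every randomised woman unless she withdraws consent to data use.
- All randomised women stay in the primary analysis.

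Where an investigator has already withdrawn a woman, recover delivery mode from the record if her consent allows, and report the number of such withdrawals by arm with reasons; 6.3.7 already requires a primary reason to be recorded when a subject withdraws.

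The cost is a short amendment and its IRB approval. Section 6.2 already takes obstetric outcomes from the electronic record, so no new data source is needed. Section 5.1.1 expects enrolment to run to June 2026, so an amendment to this version can still protect women not yet enrolled.

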6.4 Statistical Method

6.4.1 Statistical Design

Data analyses will adhere closely to the CONSORT guidelines. (27) Analyses will follow the intention-to-treat principle in which subjects will be analyzed in the group to which they were randomized, regardless of whether or not they received the assigned intervention.

6.4.2 Sample Size Considerations

1) Total sample size for the trial: The sample size for the trial is based on the primary outcome of spontaneous vaginal delivery. Therefore, the sample size of n=988 is selected for this proposed study to detect a 10% absolute increase while accounting for an expected 5% attrition rate. We then estimate, on the basis of the sample size for the primary outcome, the power we will have to detect clinically significant differences in the secondary outcomes.

Sample size estimation for primary outcome:

Detectable absolute difference	Anticipated with nipple stimulation therapy	Total Sample size Across 2 Study Groups for 90% power
15%	79%	426
14%	78%	492
13%	77%	574
12%	76%	676
11%	75%	812
10%	74%	988
9%	73%	1,222

All sample size and power estimates are based on two-tailed tests. *This is important because we will be powered to detect both increases and decreases in outcomes with intrapartum nipple stimulation therapy (intervention) versus immediate synthetic oxytocin infusion without nipple stimulation (comparator).* The expected rate of spontaneous vaginal delivery in the setting of immediate synthetic oxytocin infusion without nipple stimulation used for the sample size estimation is based on averaged institutional data from the study sites. We estimate that a total of **988** (494 nipple stimulation therapy and 494 immediate synthetic oxytocin infusion without nipple stimulation) will be sufficient to detect a **10% absolute difference** (estimated 74% versus 64%) in spontaneous vaginal delivery with 90% power (alpha of 0.05).

Justification: At first glance, the anticipated 10% or greater absolute increase in the spontaneous vaginal delivery rate in our proposed trial appears modest. On the contrary, because the potential public health impact is large, this effect size is significant. It is estimated that 40% of the *one million* women who undergo inpatient labor induction each year in the U.S. are nulliparas. Therefore, a 10% increase in spontaneous vaginal delivery translates to 40,000 more spontaneous vaginal deliveries and *40,000 fewer operative deliveries each year*. Avoiding 40,000 operative deliveries each year will have substantial impact on overall morbidity and healthcare resource utilization in the U.S. and beyond.

2) The sample size of 988 for the primary outcome will be sufficient to detect a 9.4% or 10.8% absolute difference in breastfeeding as the sole source of nutrition (BSSN) at the time of delivery hospitalization postpartum discharge with 80% power and 90% power, respectively (two-sided test, $\alpha=0.05$). This represents the difference between an expected BSSN rate of 47% in the setting of synthetic oxytocin infusion without nipple stimulation (average rate at the study sites based on institutional data) and 56.4% (with 80% power) or 57.8% (with 90% power) with nipple stimulation therapy.

3) Assuming a 15% attrition rate at 2 weeks postpartum (the time frame for our primary cost-effectiveness analysis in Aim 3), the sample size of 988 will have 90% power for detecting a standardized effect size of 0.22 for the between-group difference in cost and difference in quality adjusted life years (QALY) (two-sided test, $\alpha=0.05$). This is considered a small effect size based on conventional criteria, hence if we observe an even larger effect size, we should be sufficiently powered.

The sample size for this biospecimen trial is based on the primary comparison, specifically the difference in primary biomarkers from baseline to after 2 hours of treatment between patients performing nipple stimulation therapy and those receiving IV oxytocin. Sample size calculations are based on differences between non-laboring and laboring patients from prior reports (Table). Sample size was determined to achieve 80% power to detect a difference with a two-tailed alpha level of 0.05. The final sample size of 48 per exposure group is based on the largest sample size required (IL1beta). Therefore, there is more than adequate power for the remainder of the biomarkers of interest.

To detect a 10 mM difference in sodium concentration between the intrapartum nipple stimulation therapy group and the immediate synthetic oxytocin infusion group at 48 hours postpartum, with a standard deviation of 20 mM, 80% power, and a significance level of 0.05, a sample size of 32 participants per group is required. Accounting for an expected 30% dropout rate, we plan to recruit 46 participants per group.

To preserve the overall 5% false positive error rate, we first defined primary, secondary, and exploratory hypotheses with respect to the comparison groups. Second, we defined our hypotheses with respect to the each biomarker of interest (Table) as either disjunctive, conjunctive or individual.⁶⁴ When hypotheses are disjunctive, a rejection of one of them would yield a rejection of the overarching (joint) null hypothesis, which requires an adjustment of the alpha level for multiplicity of tests. Conceptually, since hypotheses are divided into primary, secondary, and exploratory, and individual biomarker targets identified, we created individual overarching null hypotheses where alpha-level adjustments are not required. Additionally, if we set them as conjunctive hypotheses where all the individual null hypotheses must be rejected to reject the overarching (joint) null hypothesis, the alpha level adjustment would also not be needed.

Sample Size Estimation for Biospecimen Sub-Study:

Biomarker	Reported Group Difference	Standard deviation	Sample size (per group) ^a	Estimated Effect Size ^b	Detectable Difference for n=48 ^c
Primary: Oxytocin	24.25% ^d	40.8	45	528 pg/mL	23.6%
Cytokines					
Primary: IL1b	1.56 pg/mL	2.19	48	1.56 pg/mL	1.56 pg/mL
IL6	3.34 pg/mL	2.69	23	2.5 pg/mL	1.77 pg/mL
Acute phase reactants					
Primary: PAI-1	2.27 ^e	2.655	23	23.2 ng/mL	1.76 ^e
Plasminogen	1.32 ^e	1.32	16	-3.5 mg/L	1.17 ^e
C reactive protein	1.91 ^e	1.19	21	-2.3 mg/L	1.11 ^e
Immune mediator					
Primary: ICOS Ligand	3.07 ^e	2.73	13	n/a	1.79 ^e
SFTPD	3.76 ^e	3.39	14	n/a	2.02 ^e
Metabolic					
Primary: Apolipoprotein A4	-0.79 ^e	1.19	9	n/a	-1.11 ^e
IGFBP1	-0.57 ^e	1.97	23	n/a	-1.48 ^e
Apolipoprotein E	-27.5 mg/L	23	16	-27.5 mg/L	-13.3 mg/L
Apoptosis					
ERP29	1.54 ^e	1.51	15	n/a	1.27 ^e
Prostaglandins					
PGE2	10ng/mL	4.2	3	10ng/mL	2.4 ng/mL
PGF2a	3.7 ng/mL	1	8	3.7ng/mL	0.58 ng/mL
^a Sample size (per group) that would provide 80% power to detect the reported group difference with the reported standard deviation using two-tailed tests. ^b For percent change in oxytocin, effect size was estimated based on average values in two treatment groups at the time of adequate contractions in our preliminary data. For MS data, effect size was estimated based on group differences expressed in log scale ratios converted to typical laboratory units. n/a indicates concentration in maternal circulation is unknown for estimation. Effect size refers to effect size if the study was only powered for that biomarker. ^c Detectable difference is calculated as what difference we anticipate being able to identify given the final sample size of 48. For MS counts,					

^d Based on our preliminary data

^e MS counts

